The investigator will provide a clear and concise information through oral and written instructions about the following; 1) The ice gel pad's purpose, benefits, anticipated effects and how to apply it, 2) Apply the ice gel pad on perineum after birth within 30 minutes to an hour, 3) Instruct the women to apply the ice gel pad for about 20 minutes every two hours during the first 24 hours postpartum only, 4) The perineal pad should be changed regularly every two hours to prevent infection. This session will take 30-40 minutes for each woman. Then, six hours after the ice gel pad application, assessment of experienced perineal pain will be done using Visual Analogue Scale for pain intensity (VAS) and assessment of perineal trauma condition will be done using standardized REEDA scale.

Also, six hours after birth women will receive instructions to practice pelvic floor exercises (Kegel exercises) and will be asked to perform these exercises from 6 hours postpartum and continue at home till one week. Before applying the technique, the investigator will teach the women how to recognize the accurate muscle, whereby she imagines holding passing gases or trying to stop the flow of urine midstream at the same time. The women will be taught to insert a clean finger into the vagina before practicing the exercises and if the women feeling pressure around her finger, she is on the right track, the mother also will be instructed to place a hand on her belly during the exercises to make sure that it is kept relaxed.

The investigator will perform vaginal examination while the woman is doing the pelvic floor exercises (Kegel exercises) to ensure correct use of muscles. The investigator

will instruct the women to continue contracting the muscles for about 5 seconds and then to loosen them for 5 seconds and repeat it for five times each set, perform at least five sets per day (total 25 contractions each day will be performed). The mother will be instructed to perform these five sets of exercises at the rest period between other intervention (application of cold compresses for the first 24 hours and application of warm compresses after 48 hours) with at least two hours rest between each set.

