In addition, women will be instructed to apply warm compresses on perineal trauma 48 hours postpartum +at home. This will be done by using a clean pad soaked in warm water and squeezed to remove excess water then placed gently on the perineum, the warm compresses will be applied for 15 minutes three times per day (every 8 hours), and water in the bowl will be replaced with every application. Women will be asked to apply warm compresses on perineal trauma from 48 hours postpartum till one week. Also, before discharge each woman will have an explanation of Visual Analogue Scale for pain intensity (VAS) and they will be trained to indicate level of perineal pain using it. This session will take 30-40 minutes for each woman.

Intervention for the control group: The control group will receive the routine hospital care only. Then, six hours after delivery, assessment of experienced perineal pain will be done using Visual Analogue Scale for pain intensity (VAS) and assessment of perineal trauma condition will be done using standardized REEDA scale.

Follow up and monitoring: Follow up will be done by telephone calls and by postpartum visit at the seventh day:

For intervention group follow up by telephone call will be done at 24 hours to assess the following; degree of perineal pain using Visual Analogue Scale for pain intensity (VAS),

the women compliance with ice gel pad application for the first 24 hours, the women's need for additional analgesia and assess women's postpartum difficulty with performing functional activities as turning/ rolling in bed, getting out of bed, sitting, walking, defecation and urination using Visual Analogue Scale(VAS) for rating functional activities.

Also, telephone follow up will done at third and fifth day postpartum to assess degree of perineal pain using Visual Analogue Scale for pain intensity (VAS) and assess women's postpartum difficulty with performing functional activities as turning/ rolling in bed, getting out of bed, sitting, walking, defecation and urination using Visual Analogue Scale(VAS) for rating functional activities. The investigator will also assess mother compliance with the performance of pelvic floor exercises (Kegel exercises) and application of perineal warm compresses using postpartum follow up sheet.

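### On the stated times, the study arm's six-hour pain and REEDA scores fall 30 to 60 minutes after Kegel teaching with a vaginal examination is due; no order is stated, and no such procedure is described for controls

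*Combined protocol and SAP*

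**What the plan says.** The relevant text is in the protocol's Procedure section, under the interventions for the study group and the control group.

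- **First pad, study arm:** "Apply the ice gel pad on perineum after birth within 30 minutes to an hour".
- **Repeat pads:** women are told to "apply the ice gel pad for about 20 minutes every two hours during the first 24 hours postpartum only". The text does not say whether the interval runs from the start of one pad to the start of the next, or from removal to the next start.
- **Six-hour scoring, study arm:** "Then, six hours after the ice gel pad application, assessment of experienced perineal pain will be done", with REEDA at the same point.
- **Kegel teaching, study arm:** "Also, six hours after birth women will receive instructions to practice pelvic floor exercises (Kegel exercises"). The woman is taught to check the contraction with her own finger, and "The investigator will perform vaginal examination while the woman is doing the pelvic floor exercises (Kegel exercises) to ensure correct use of muscles". The examination has no clock time of its own.
- **Six-hour scoring, control arm:** "Then, six hours after delivery, assessment of experienced perineal pain will be done using Visual Analogue Scale", again with REEDA. Controls receive routine hospital care, which is not described further.

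Under Outcome measures, pain severity and delayed healing are both primary, and no time point is named. The Statistical plan compares both scores by t test, also without naming a time.

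**The concern.** Two study-arm events share a six-hour label but run on different clocks: the teaching is timed from birth and the scoring from the pad. On those clocks, an intrusive procedure on freshly injured tissue comes due shortly before both primary outcomes are scored. It is plausible, though the documents do not say so, that such an examination briefly raises reported pain or alters what REEDA records. If so, the six-hour difference between arms would include discomfort from a teaching procedure as well as the effect of the care package.

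The second issue is the point in the cold cycle. A woman scored as a pad comes off and a woman scored well after the last pad are in different states. The plan neither fixes nor records which applies.

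Because no primary time point is named, the six-hour comparison could be reported as a primary result. If order and timing are not recorded, neither issue can be examined afterwards.

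**Working it through.** The plan gives no figure to reproduce here, so the check is clock arithmetic from its stated times. Let t0 be the start of the first pad, 0.5 to 1.0 h after birth. I take the pad application from which scoring is timed to be the first one.

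**Scoring against teaching.** Study-arm scoring = t0 + 6 h.

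| Event (hours after birth) | t0 = 0.5 h | t0 = 1.0 h |
|---|---|---|
| Kegel teaching due | 6.0 | 6.0 |
| Control scoring | 6.0 | 6.0 |
| Study-arm scoring | 6.5 | 7.0 |
| Study-arm scoring minus teaching | 30 min | 60 min |

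Study-arm scoring is also 30 to 60 minutes later after birth than control scoring. If the 30 to 40 minute session length given at the end of the study-group teaching text covers the Kegel instruction (an assumption), scoring falls between 10 minutes before that session ends (30 − 40) and 30 minutes after it ends (60 − 30).

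**Scoring against the ice-pad cycle, each pad lasting about 20 minutes.**

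- Start-to-start reading: pad k starts at t0 + 2(k − 1) h. Pad 4 starts at t0 + 6 h, the scoring time. Pad 3 starts at t0 + 4 h and ends at t0 + 4 h 20 min, 100 minutes before scoring.
- Removal-to-start reading: the cycle is 2 h 20 min. Pad 3 starts at t0 + 4 h 40 min and ends at t0 + 5 h, about 60 minutes before scoring. Pad 4 is due at t0 + 7 h, about 60 minutes after scoring.

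**If the study arm were scored at 6.0 h after delivery, as controls are.** Time since pad 3 ended would be 6 h − (t0 + 4 h 20 min) = 70 or 40 minutes on the first reading. On the second it would be 6 h − (t0 + 5 h) = 30 or 0 minutes. A common clock aligns the arms but does not fix the point in the cold cycle, so the time since the last pad still has to be recorded.

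**Reach.** Post-baseline VAS is taken at six hours, 24 hours and days 3, 5 and 7, so 1 of 5 times is affected. Post-baseline REEDA is taken at six hours and day 7, so 1 of 2.

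**Scale, for illustration only.** The documents give no size for an examination effect. Suppose it raised every study-arm score by a fixed amount and worked against a true benefit of 0.8 SD (the plan's 80% effect size read as d = 0.8). With 50 per arm and a two-sided 0.05 test, the noncentrality is 5 × (0.8 − shift). Power at six hours would fall from 97.7% with no shift to 93.4%, 84.4%, 69.7% or 31.8% for shifts of 0.1, 0.2, 0.3 or 0.5 SD. These shifts are assumed, not estimated.

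**The case against.** The strongest reply is that the plan never places the score after the examination. The study-group text describes VAS and REEDA first and only then turns to Kegel teaching, which is the order one would want. Six hours is stated for the instructions, not for the examination. The Description of the protocol starts the exercises after six hours, and the background gives a window of six to twelve hours, once the woman is ready. This stands. The 30 to 60 minute gap is what the stated times imply, not a prescribed sequence. But narrative order and stated times point in opposite directions, and nothing settles which governs.

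A reader might also infer that scoring coincides exactly with the fourth pad. That holds only on the start-to-start reading.

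A reader might call the cold effect an artefact that biases the comparison. The documents do not support that. Reducing pain and edema is the pad's stated purpose, so relief from it is part of what is being tested. What remains is that the point in the cycle is unspecified and can vary between women.

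Finally, routine care is not described, so it cannot be asserted that controls have no examination or cold treatment, only that none is described for them. The documents also contain no evidence on how far an examination shifts VAS or REEDA.

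**Conclusion.** The concern holds in a limited form. On the stated times, both primary outcomes are scored in the study arm 30 to 60 minutes after teaching that includes a vaginal examination is due. No order is stated, and no counterpart is described for controls. A short-lived, one-arm measurement effect could therefore enter the six-hour comparison. The point in the ice-pad cycle at scoring is also left open.

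This rests on three assumptions: that scoring is timed from the first pad, that teaching begins at its stated hour, and that the examination takes place within it.

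A reader might infer that the six-hour scores do capture examination and cold effects, or that the trial's primary result is biased. The documents support neither. Examination discomfort could raise scores and recent cold could lower them, so no net direction or size can be derived. The 24-hour and day 3, 5 and 7 assessments are unaffected, and six hours is not named as the primary time. The change is still worth making, because it costs little and the problem cannot be repaired later if timing goes unrecorded.

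**What to change.** Reconcile the two six-hour clocks in the study-group text with the control-group text:

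1. Score VAS and REEDA in both arms at the same stated time from delivery.
2. State that both are completed before the Kegel teaching, the self-check and the vaginal examination.
3. Record the time of scoring and, in the study arm, the time since the last pad was removed. State whether the pad interval runs from start or from removal, so that this field can be interpreted.

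This specifies measurement order only. The pad and exercise regimens remain for the sponsor to state.

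The cost is a few sentences and the time fields, with no extra visit. The six-hour contact needs one agreed schedule, and teaching may start slightly later, after the assessment. Keeping the control arm's existing scoring time for both arms would keep that delay short. Keeping scoring at 6.5 to 7.0 h while requiring it to come first would hold the teaching back 30 to 60 minutes, so a sequencing sentence without the clock reconciliation is not enough.

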Tool (B) Visual Analogue Scale for Pain Intensity (VAS): It is a standardized linear scale developed by Freyd et al., (1923). It is a self-reported 10 cm horizontal line which represents the subjective estimation of pain intensity. It comprises 0-10-point numerical scale, the two opposite ends representing no pain to severe pain as follows: no pain (0), mild pain (< 4), moderate pain (4 - <8), and sever pain (8-10). This tool is valid and reliable, test-retest reliability coefficient of the VAS has been demonstrated in several studies as $r =0.62$ (Derya, Ergul, Senol, &Aslan, 2017).

Tool (C) Visual Analogue Scale (VAS) for rating functional activities: This tool is adopted from Karakaya et al.,(2012), the difficulty with performing functional activities as (turning/ rolling in bed, getting out of bed, walking, sitting, defecation and urination) will be evaluated by using horizontal 10 cm visual analogue scale for each functional activity, the scale will be applied six times to measure the difficulty with each activity (VAS will be

marked by the women). The scoring for each activity will be as follows: no difficulty (0), mild difficulty (< 4), moderate difficulty (4 - <8), and sever difficulty (8-10). The total score will be recorded (0-60 point), the lowest score (0) indicate no difficulties and the maximum score (60) indicate maximum difficulty. The total score will be interpreted as the following no difficulties (0), Mild difficulties (1 - < 24), Moderate difficulties (24 - < 48), Sever difficulties (48-60). This tool is valid and reliable, test-retest reliability coefficient has been demonstrated as $r = 0.82$ (Karakaya et al., 2012).

Tool (D) Standardized REEDA Scale: This tool is adopted from Davidson (1974), REEDA scale will be used to assess condition of perineal trauma. REEDA scale is a descriptive scale having a four point categorical score (0-3) that measures five components associated with the healing process of perineal trauma. This includes: Redness, Edema, Ecchymosis, Discharge and Approximation of sutures. The total score ranged from 0 to 15 and categorized as the following; 0 to 2 cm good wound healing with no infection, 3 to 5 cm moderate wound healing, 6 to 8 cm mild wound healing, and 9 to 15 cm poor wound healing with infection . This tool is valid and reliable, test-retest reliability coefficient of the REEDA scale has been demonstrated as $r = 0.70$ (Farrag, Eswi, & Badran, 2016).

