Initial Assessment: Initial assessment for women in both groups (study & control group) will be carried out in relation to body mass index (BMI), type of perineal trauma after delivery (episiotomy, or tears), degree of perineal tear (1st or 2nd degree tear), and assessment of perineal trauma condition will be done using standardized REEDA scale . Also, women will be asked to indicate the degree of perineal pain using Visual Analogue Scale for pain intensity (VAS).This assessment will take 15 minutes for each woman.

Intervention:

Intervention for the study group: For the study group the intervention will be according to a designed protocol of care that entails; 1) Application of ice gel pad on perineal trauma for the first 24 hours post partum; 2) Performance of pelvic floor exercises (Kegel exercises) from six hours till one week postpartum; 3) Application of warm compresses after 48 hours and through the first week postpartum. The investigator will perform demonstration and then redemonstration by the women on each intervention will be done. A designed booklet (developed previously) that explains each intervention will be given to each woman.

Immediately after delivery (within 30 minutes to one hour after delivery), an ice gel pad will be applied to perineal trauma. It will be available in an individual package(every woman will alternate between two ice gel pads); each gel pad will have fixed standardized diameter (an approximately 5 cm width, 23 cm length, and 1.5 cm thickness) and approved by Egyptian ministry of health. It will be kept in the freezer for 45–60 minutes and

will be removed when frozen. Then, it will be wrapped in a sterile pad and applied to cover the perineum and anal region. The pad will be compatible with the anatomical structure of the perineum.

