For control group follow up by telephone call will be done at 24 hours to assess degree of perineal pain using Visual Analogue Scale for pain intensity (VAS), the women's need for additional analgesia and assess women's postpartum difficulty with functional activities as turning/ rolling in bed, getting out of bed, sitting, walking, defecation and urination using Visual Analogue Scale (VAS) for rating functional activities. Also, telephone follow up will be done at third and fifth day postpartum to assess degree of perineal pain using Visual Analogue Scale for pain intensity (VAS) and assess women's postpartum difficulty with performing functional activities as turning/ rolling in bed, getting out of bed, sitting, walking, defecation and urination using Visual Analogue Scale (VAS) for rating functional activities.

Then, a final postpartum follow up visit for both groups at the seventh day will be conducted for assessment of perineal trauma condition and healing process using

standardized REEDA scale and assess the degree of perineal pain using Visual Analogue Scale for pain intensity (VAS).

References

Davidson, N. (1974). REEDA: evaluating postpartum healing. *J Nurse Midwifery*. 1974; 9:6–9.

Derya, K., Ergul, Senol, &Aslan, E. (2017). The Effects of Cold Application to the Perineum on Pain Relief After Vaginal Birth, *Asian Nursing Research*, Volume 11, Issue 4, Pages 276-282, ISSN 1976-1317.

El-Saidy, T. M. K., Abou shady, R. M. N., &Soliman, H. F. A. (2018). Effect of Applying Crushed Ice Gel Pads on Episiotomy Pain and Wound Healing Among Postpartum Primiparous Women. *ijnd* 2018, 8, 19-29.

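### Training in the pain VAS before discharge is written only for the study group, yet both arms then rate pain, a primary outcome, by telephone

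*Combined protocol and SAP*

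**What the plan says.** All references are to the combined protocol and SAP.

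- **Study group.** The Procedure section on the study-group intervention opens "Intervention for the study group: For the study group the intervention will be according to a designed protocol of care that entails" three components, and it runs until the control-group heading. Near its end, after the warm-compress instructions and before that session's duration, it says that "before discharge each woman will have an explanation of Visual Analogue Scale for pain intensity (VAS) and they will be trained to indicate level", meaning how much pain they have.
- **Control group.** The next paragraph begins "The control group will receive the routine hospital care only". It adds assessments of pain and of the wound at six hours, and nothing on explaining the scale.
- **Before any call.** Under Initial Assessment, which covers both groups, "women will be asked to indicate the degree of perineal pain using Visual Analogue Scale for pain intensity (VAS"). Pain is rated again six hours after the ice pad is applied (study group) or six hours after delivery (control group).
- **Telephone ratings.** Under Follow up and monitoring, both groups are called at 24 hours, day 3 and day 5 for pain and for six functional activities. For controls, for example, "follow up by telephone call will be done at 24 hours to assess degree of perineal pain". Day 7 is a visit, at which pain and REEDA are recorded but the functional scale is not listed.
- **The instruments.** Tool (B), for pain, is a self-reported 10 cm line, also described as a 0-10 numerical scale. Tool (C), for function, is "evaluated by using horizontal 10 cm visual analogue scale for each functional activity", and it is "marked by the women".

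**The concern.** Severity of perineal pain is one of two primary outcomes. The woman reports it herself, no blinding is described, and each woman knows which care she receives. In that setting, preparation for the measurement should be the same in both arms. Here it is attached to one arm's teaching programme. A woman shown again how to place her pain on the scale, during a session about treatments meant to relieve that pain, may use the scale differently from one who was not. Any such change would enter the between-arm comparison of pain scores and could not be separated from a treatment effect. The Statistical plan's t test compares the groups' scores as they stand and cannot remove it.

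The other primary outcome, wound healing on REEDA, is not self-rated and is not touched by this point.

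**Working it through.** The plan gives no figure on this point to reproduce. The check is a reading of every mention of the two scales, by arm and time.

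**1. Preparation and ratings, as written**

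| Step | Study group | Control group |
|---|---|---|
| Initial assessment, in person | pain VAS | pain VAS |
| About six hours, in person | pain VAS | pain VAS |
| Explanation and training, pain VAS, before discharge | yes | not described |
| Training, functional VAS | not described | not described |
| 24 hours, day 3, day 5, telephone | pain and functional VAS | pain and functional VAS |
| Day 7, visit | pain VAS | pain VAS |

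The arms differ in one row only.

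**2. How many ratings are involved**

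- Pain: 2 in person before the calls + 3 by telephone + 1 at the visit = 6 ratings, of which 3 are by telephone.
- Function: 6 activities × 3 calls = 18 ratings, all by telephone. The rows above show no difference in preparation between arms for these.

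**3. Does the training sentence cover both arms?**

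It refers to each woman, which could be read as everyone in the trial. Three features of the text point the other way.

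- It lies within the study-group section, between two sentences about a study-group session.
- The same phrase is used elsewhere in that section for things only study women receive, such as the booklet on the interventions and the ice-pad teaching session.
- Where the protocol means both arms it says so, as at the interview, the initial assessment and the day 7 visit.

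Staff who followed the text would therefore train one arm.

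**4. How a telephone rating is obtained**

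Both tools are lines, and the caller cannot see a mark on a line. The numerical description under Tool (B) would allow a spoken number for pain, but the protocol does not say that this is the method. Tool (C) also carries numerical cut-points, but its text has the woman mark the line. This gap is the same in both arms.

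**5. Can the bias be sized?**

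No. That would need the shift in reported pain caused by the extra training, and the SD of the pain score. The documents give neither.

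Purely to show sensitivity, take no true effect and an assumed shift. The standardised difference is d = shift / SD. The two-sided 5% t test with 50 per arm has noncentrality d × √(50/2) = 5d on 98 degrees of freedom.

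| Assumed shift (cm) | Assumed SD (cm) | d | Rejection rate |
|---|---|---|---|
| 0.25 | 2.5 | 0.10 | 7.9% |
| 0.5 | 2.0 | 0.25 | 23.6% |
| 0.5 | 1.5 | 0.33 | 37.9% |

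These rates only restate the assumptions and are not an estimate for this trial.

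**The case against.** The strongest reply is that the sentence may simply be misplaced. It is a measurement instruction, not a treatment step, and both groups are telephoned for the same rating, so it may have been meant for everyone. The documents do not exclude this. It remains a reason to correct the text, because the text is what staff will follow.

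Four stronger readings are tempting, and the documents do not support them.

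- **That controls are untrained.** They rate pain on the scale in person twice before the first call, as study women do. The difference is one further step.
- **That function is affected in the same way.** The training names only the scale for pain intensity. Its absence for the functional scale is common to both arms.
- **That telephone use of a line itself biases the comparison.** Any difficulty in reading a line by telephone applies equally to both arms. It is a question of measurement error and mode of administration.
- **That the false-positive rate is known to be inflated, say to 8-38%.** The arithmetic is right but the inputs are assumed. Nothing in the documents says that the training would move the mean, or in which direction. It could as easily hide a benefit as create one.

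Nor do the documents say who gives the training. That it is the investigator who teaches the interventions is an inference from the surrounding text.

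**Conclusion.** The point holds in a limited form. As written, study women receive one preparation step for the pain scale that control women do not, ahead of three telephone ratings of a self-reported primary outcome. This rests on where the sentence is placed and on the control group's routine-care-only wording. It would fall away if the sponsor confirmed that controls get the same explanation. No size or direction of bias can be claimed. Two related gaps are shared by the arms: no described training in the functional scale, and no stated way of taking a line rating by telephone. The case for changing the text is that the difference is avoidable and nearly free to remove. It does not rest on any demonstrated distortion.

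**What to change.** - Move the explanation of the scale, with a practice rating, to Initial Assessment. Use one script for both groups, covering both the pain and the functional scale.
- Give it before the envelope is opened where possible. The Procedure lists randomisation ahead of the initial assessment, so this means changing the order. If that is not practical, the common script still removes the written difference.
- State one method for telephone ratings, identical in both arms. A spoken 0-10 number would be consistent with the description of Tool (B). The same printed lines for every woman are an alternative, but sheets can be lost or filled in afterwards, so they are optional.
- If data have already been collected, report whether control women received the explanation and how the telephone ratings were taken.

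The cost is a moved and slightly longer paragraph, and a few extra minutes with each control woman.
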